In 2014, the FDA approved an over-the-counter disposable intravaginal device as another nonsurgical treatment for SUI. This device, the Poise Impressa®, is made of a non-absorbable nylon mesh that covers a core with 4 support poles made of resin and is housed in an applicator, similar to that of a tampon applicator(5). It is currently marketed as an over the counter non-surgical treatment of SUI, providing an effective alternative to physical therapy or surgery(6). Ziv et al conducted the initial study on this device, examining it over a 28 day period (comprised of a 14 day trial run followed by a 14 day observation period)(5). The authors found that 85% of participants experienced a  $\geq 70\%$  reduction in pad weight when using the device over the 14 day observation period. They also found that Poise Impressa® use was associated with an improvement in quality of life and had high patient satisfaction (5, 7).

The differences in these two devices are important and may result in major differences in patient satisfaction, compliance, and cost of use. The Poise Impressa® can only be worn up to 12 hours per day and is single use only, whereas the continence pessary can be worn continuously and is both reusable and reimbursable by insurance. To date, there has not been a comparative effectiveness trial performed to address this gap in knowledge. We aim to conduct a randomized comparative effectiveness trial of the continence pessary and the Poise Impressa® in order to provide patients and providers knowledge of the best nonsurgical treatment for women with SUI. We hypothesize that a physician fit continence pessary will provide greater subjective improvement in SUI symptoms, greater improvement in quality of life, greater patient satisfaction, and be lower cost as compared to the Poise Impressa®.

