## II. SPECIFIC AIMS

**Specific Aim 1: To compare SUI symptom improvement between a continence pessary and the Poise Impressa® device.** Improvement will be assessed using the Patient Global Impression of Improvement (PGI-I), a validated questionnaire assessing symptom changes(8).

**Specific Aim 2: To compare quality of life, patient satisfaction, ease of device use, likelihood of continued use, and rates of adverse events between the continence pessary versus the Poise Impressa®.** We will use validated questionnaires to assess participants' quality of life (9, 10). We will monitor for adverse events that are related or possibly related to the study device such as pain, vaginal bleeding, infections, and lacerations. We will use a Likert scale to assess patient satisfaction, ease of device use, comfort, and likelihood of continued use.

**Specific Aim 3: To evaluate cost of use associated with each device.** We will use cost of clinic visits and the cost of the device(s) to calculate estimated costs associated with device utilization.

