**Cost analysis:** For the Poise Impressa® device, cost calculations will include cost of sizing kit and devices, as well as costs associated with any refits. For the continence pessary, cost calculations will include the cost of the device, initial fitting visit and any additional clinic visits. Cost will be extrapolated to estimate annual cost of use for each device.

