#### **Participant Cost**

There will be no out of pocket costs to the participant to participate in this study. The initial visit to the office is billed to the insurance company as this is a visit that is scheduled by the participant for a visit to address one or more of their pelvic floor disorders. Participants interested in non-surgical management of SUI are identified and offered enrollment if they meet all necessary criteria. Patients would receive a continence pessary as part of routine care if they were not enrolled in the study. Participants that are randomized to the continence pessary arm will have their insurance charged as part of standard of care for the device, intervention visit, week 2 visit, and any unscheduled visits. As week 4 is considered a study visit, they will not be charged for this visit. Participants that are randomized to the Poise Impressa® arm will have their devices provided free of cost, along with their study visits (intervention visit, week 2, and week 4) since it is not standard of care to provide these devices or have follow up visit as patients are able to purchase these over-the-counter without physician guidance. Any unscheduled visits due to an adverse event will be considered a billable visit since a patient would come to the office for this problem if they were using this device outside of the study.

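### The cost lists count adverse-event clinic visits for the pessary but do not list them for Impressa, and the rule for extrapolating four weeks to a year is not stated

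*Combined protocol and SAP*

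**What the plan says.** Specific Aim 3 defines cost in the same terms for both devices: "We will use cost of clinic visits and the cost of the device(s) to calculate estimated costs associated with device utilization". The Background hypothesises that the pessary will "be lower cost as compared to the Poise Impressa".

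The Cost analysis paragraph (Methods, under the secondary outcomes) then gives each arm its own list. For Impressa, "cost calculations will include cost of sizing kit and devices, as well as costs associated with any refits". For the pessary, "cost calculations will include the cost of the device, initial fitting visit and any additional clinic visits". It ends: "Cost will be extrapolated to estimate annual cost of use for each device". No formula, unit-cost source or measure of device use follows.

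Participant Cost says that pessary users' insurance is charged for the device, the fitting visit, the week 2 visit and unscheduled visits, and that the week 4 visit is not charged. Scheduled Impressa visits are free because women can buy that device themselves without seeing a clinician. For Impressa it adds: "Any unscheduled visits due to an adverse event will be considered a billable visit". The reason given is that a woman using the device outside the trial would also come in for such a problem.

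**The concern.** The pessary list ends in an open category that takes in every further clinic visit, whatever the reason. The Impressa list ends at refits. An analyst who follows the two lists would count an adverse-event visit in one arm and leave it out in the other. The protocol's own account of ordinary care says that this visit happens, and is billed, in both.

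The extrapolation sentence adds a second uncertainty. The Background describes the pessary as reusable and Impressa as single-use, so most pessary cost falls at the start and most Impressa cost recurs. How four weeks become a year can therefore decide which device looks cheaper. Cost is one of three specific aims and carries a directional hypothesis, so both rules should be fixed before anyone sees the cost data.

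**Working it through.** The documents state no cost figure, so there is none to reproduce. The first step sets the passages side by side. The second and third use assumed prices and rates, for illustration only.

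**1. What each list covers**

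- Device: listed in both arms, with the sizing kit added for Impressa.
- Scheduled fitting and week 2 visits: costed for the pessary, not for Impressa. Participant Cost explains this by over-the-counter purchase.
- Refits: covered in both arms.
- Unscheduled adverse-event visit: covered for the pessary by the open category, not listed for Impressa. Nothing explains this, and Participant Cost points the other way.

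Only the last item is an unexplained inequality.

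**2. Size of the omission**

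Understatement of mean Impressa cost = p × C, where p is the proportion of Impressa participants with an adverse-event visit in four weeks and C is the price of the visit. Assumed: p from 2% to 20%, C from $100 to $200.

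- Low: 0.02 × $100 = $2 per participant per four weeks.
- High: 0.20 × $200 = $40 per participant per four weeks.

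The annual effect depends on a rule that the plan does not give. If these visits occur only early in use, it stays at $2 to $40. If they are scaled linearly by 365/28 = 13.04, it is $26 to $521.

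**3. Why the annualisation rule matters**

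Let F be the one-time pessary cost (device, fitting, week 2 visit), k the sizing kit and r the cost of four weeks of Impressa devices. Leave unscheduled visits aside and round the factor to 13.

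- One-time items counted once: pessary F, Impressa k + 13r. The pessary is cheaper if F < k + 13r.
- Whole four-week total scaled: pessary 13F, Impressa 13(k + r). The pessary is cheaper only if F < k + r.

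The two readings disagree whenever F lies between k + r and k + 13r. No price is needed for that result.

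With assumed prices and the factor 13.04:

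- Pessary: device $50 to $100, fitting $100 to $200, week 2 visit $100 to $200, so F = $250 to $500. Counted once, it stays there. Scaled, it becomes $3,259 to $6,518. Without the week 2 visit, the low end is $150, or $1,955 scaled.
- Impressa: $1 to $2 per device, 7 to 28 devices in four weeks, kit $5 to $10. Kit counted once: $5 + 13.04 × $7 = $96, up to $10 + 13.04 × $56 = $740. Everything scaled: 13.04 × $12 = $156, up to 13.04 × $66 = $860.
- Excess from scaling one-time items: 12.04 × F = about $3,009 to $6,018 for the pessary, and 12.04 × k = about $60 to $120 for the Impressa kit.

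One case of reversal: F = $250, k = $5, r = $28. Counted once, the pessary costs $250 and Impressa $370. Scaled, the pessary costs $3,259 and Impressa $430.

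**The case against.** Both lists say what the calculations will include, which need not be exhaustive. Nothing states that adverse-event visits are left out for Impressa, and Participant Cost is about who is billed, not about what the cost analysis counts. An analyst guided by Specific Aim 3 might include them. This stands to the extent that the omission cannot be called a deliberate exclusion. But one list is open and the other is not, and following them as written gives unequal totals.

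Costing the fitting and week 2 visits only for the pessary is justified by how each device is obtained. That stands fully.

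A reader might infer that the plan multiplies four-week totals by 13. It does not say so. Since the pessary is described as reusable, counting it once is the more natural reading, and the large inflation then disappears. A reader might also infer that only the pessary has start-up costs. That is wrong: the sizing kit and refits are on the Impressa list and would be inflated too, though by less under the assumed prices.

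Finally, cost is a secondary matter here. It does not touch the primary outcome, the sample size or safety.

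**Conclusion.** The unequal treatment of unscheduled adverse-event visits is a real inconsistency between the Cost analysis paragraph on one side and Participant Cost and Specific Aim 3 on the other. Followed as listed, it understates Impressa cost by p × C: $2 to $40 per participant per four weeks under assumed rates of 2% to 20% and prices of $100 to $200. The documents supply neither input.

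The annualisation point is missing detail and not a stated error. It belongs in the same edit because two readings of one sentence can rank the devices in opposite orders.

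A reader might go further and conclude that the annual comparison is biased against the pessary overall. The documents do not support that. Taken alone, the visit omission works against the pessary, but clinic visits and any pessary replacement after week 4 are not observed, and costing Impressa devices supplied instead of devices used would raise Impressa cost. Even with one-time items counted once, the assumed ranges overlap ($250 to $500 for the pessary, $96 to $740 for Impressa), so they do not show which device is cheaper.

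**What to change.** Revise the Cost analysis paragraph as follows.

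- Count unscheduled visits, for a refit or a device-related adverse event, by the same rule in both arms. Leave the scheduled Impressa research visits uncosted, citing the reason in Participant Cost.
- Count one-time items once: pessary, fitting visit and scheduled week 2 visit in one arm, sizing kit in the other. Scale only recurring items to a year, and state the factor.
- Say how unscheduled visits are annualised: counted once, or scaled.
- State the unit-cost sources and the measure of Impressa device use. That measure must exist for every participant. In the Interval Study Questionnaire, the question on days of wear is printed under the branch for women who had a period, so women without menses may not be asked it. Ask everyone, or use another count of devices used.

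The cost is a few sentences and slightly more analysis work. Unscheduled visits must also be captured in both arms: the plan records adverse events in the research database but does not say that every unscheduled visit is recorded. No extra study visit is needed.

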### Study Visits

The study will consist of a four-week active observation period. Subsequently, there will be a follow up period consisting of a phone call at 6 months. (Figure 1: Study Flow Chart).

**Figure 1. Study Flow Chart**

#### *Baseline Visit*

Patients who are interested in the study will be consented and screened for inclusion/exclusion criteria. If there is concern for a urinary tract infection or vaginal infection, as previously defined in the exclusion criteria, further baseline data collection will be deferred until evaluation and treatment has been completed.

Participants will complete a demographics questionnaire and their medical and surgical history will be abstracted from electronic medical records. POP-Qs completed within the last year may be used to confirm study criteria; otherwise a new POP-Q must be completed. Participants will complete the MESA, UDI-6, IIQ-7, and FSFI questionnaires, and will then be randomized to an intervention group. Participants will be scheduled for their week 0 fitting visit, and then sent home with instructions to complete a 3-day bladder diary.

#### *Fitting Visit (Week 0)*

As described above participants will either undergo a pessary fitting or receive the Poise Impressa® fitting kit to determine proper sizing and the Poise Impressa® group will be given a two-week supply of the appropriately sized devices.

#### *Week 2 Visit*

All participants will complete the Interval Study Questionnaire and report on adverse events. All patients randomized to the continence pessary will undergo a pelvic exam per routine clinical practice to be assessed for possible refitting. Occurrence of any adverse events will also be assessed at that time. Participants randomized to the Poise Impressa® device will meet with research staff to assess size and if needed undergo resizing and will receive an additional 2-week supply of appropriately sized devices. For those participants in the Poise Impressa®, only those reporting symptoms concerning for adverse events will undergo pelvic exam by a clinical provider, otherwise an exam will be deferred in this group.

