**Secondary outcomes:**

**Quality of life (QoL):** Participants' QoL will be assessed with the following three validated questionnaires:

1. Urogenital Distress Inventory (UDI-6)(9, 12): This short form 6-item questionnaire measures urinary incontinence symptom bother.
2. Urinary Incontinence Impact Questionnaire (IIQ-7)(9, 12): This short form 7-item questionnaire measures the functional impact of urinary incontinence.
3. Female Sexual Function Index (FSFI)(13): This 19-item questionnaire is used to assess sexual functioning in women.

These questionnaires will be completed by participants at baseline and then again at the end of the 4-week study period. A change score will be calculated by subtracting the two scores.

**Interval Study Questionnaire:** Participants will complete this questionnaire at weeks 2 and 4. It consists of questions addressing menstrual status, device use, adverse events, and Likert scale questions assessing *device satisfaction, ease of use, comfort, and likelihood of continued use*. The questions will consist of the following:

- "Did you have your period during the last 2 weeks?"
  - If yes, "During the last two weeks, how many days were you on your period?" and "During the last two weeks, how many days did you wear your device?"
- "On average, how many hours a day did you wear your device?"
- "How satisfied were you with the device?" Participants may respond with "completely satisfied," "somewhat satisfied," or "not at all satisfied," "(14)." Responses include "completely comfortable," "somewhat comfortable," "not at all comfortable."
- "In general, how comfortable is the device?" Responses include "completely comfortable," "somewhat comfortable," "not at all comfortable."
- Ease of use will be assessed by asking "how easy/difficult was the device to use?", "how easy/difficulty was the device to insert?" and "how easy/difficult was the device to remove?" Responses will include "very easy," "easy," "somewhat easy," "somewhat difficult," "difficult," "very difficult."
- Likelihood of continued use will be assessed using the same Likert scale ranging from "strongly disagree" to "strongly agree" and asking participants to rate their level of agreement with the statement "I would continue to use this device in the future."

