- Participants will also be asked, "If you had a friend or family member with stress urinary leakage, would you recommend this device to them?" Responses included "definitely would recommend," "probably would recommend," neutral or unsure," "probably would not recommend," "definitely would not recommend."
- Participants will also be asked if they have experienced any of the following: vaginal discomfort/pain, vaginal bleeding, vaginal infection, vaginal abrasion or laceration (cut in the vaginal tissues), urinary tract infection (bladder infection), other (with space to write in a response)

Additionally, participants will receive a phone call at 6 months during which general information regarding current device use and satisfaction will be collected via the follow-up questionnaire below. The PGI-I will also be administered verbally during these follow-up calls.

**Follow-Up Questionnaire:** Participants will complete this questionnaire at 6 months with a follow up phone calls and asked to respond to the following questions:

- "Are you still using the device provided to you during the study?"
  - If "yes", they will be asked "How satisfied are you with your current treatment?" Responses include "completely satisfied", "somewhat satisfied", or "not at all satisfied"
  - If "no", they will be asked several questions including:
    - Why are you not using the device? (select all responses that apply): "the device was too difficult to use", "the device did not work", "the device was too expensive", "I am using a different treatment," "I am not bothered by my leakage" or "Other".

- Are you using another treatment? If yes, "what treatment are you using?" with options of pessary, impressa, physical therapy, surgery, other
- They will also be asked the PGI-I

[figure not shown]
**Adverse events (AEs):** Potential AEs of interest include vaginal pain attributed to device use, vaginal bleeding, vaginal infection, vaginal abrasion/laceration, and urinary tract infection. Participants will be instructed to call and report any/all adverse events to research personnel and clinical staff. All AEs will be reported to the IRB of the institution at which the AE occurred (if required by site reporting guidelines), recorded in the research database, and if needed the patient will be scheduled for a clinical assessment. AEs will be assessed at each clinical/research visit and reported with study outcomes.

[figure not shown]

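### Aim 2 compares adverse event rates, but at week 2 every pessary user is examined and Impressa users only on symptoms; the plan should record how each event was found and compare like with like

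*Combined protocol and SAP*

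**What the plan says.** Specific Aim 2 sets out to compare "rates of adverse events between the continence pessary versus the Poise Impressa", along with quality of life, satisfaction and ease of use.

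The Week 2 Visit section treats the arms differently. For the pessary: "All patients randomized to the continence pessary will undergo a pelvic exam per routine clinical practice to be assessed for possible refitting", followed by "Occurrence of any adverse events will also be assessed at that time". Impressa users meet research staff about sizing, and "only those reporting symptoms concerning for adverse events will undergo pelvic exam by a clinical provider"; for the others no exam is done at that visit.

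The remaining AE detection is common to both arms:

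- Interval Study Questionnaire: "Participants will complete this questionnaire at weeks 2 and 4". It has an AE item: "Participants will also be asked if they have experienced any of the following", with a list that includes vaginal infection and abrasion or laceration.
- Adverse events paragraph: "Participants will be instructed to call and report any/all adverse events to research personnel and clinical staff".
- Week 4 Visit/End of Study: every participant has a pelvic exam to look for AEs.

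On reporting, the adverse events paragraph says "AEs will be assessed at each clinical/research visit and reported with study outcomes". The Statistical Analysis section assigns categorical variables to chi-square or Fisher's exact tests. It does not say how AEs found by different routes enter the comparison.

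**The concern.** A vaginal abrasion or infection can be present without symptoms. At week 2 such a finding would be seen in a pessary user and missed in an Impressa user who reports nothing. If it has gone by week 4, or the woman has left the study, it counts in one arm only. Two devices with the same true harm could then show different AE rates because one arm was looked at more often.

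At stake is the safety part of a comparative effectiveness message. If the route of detection is not recorded as the data come in, nobody may be able to say later whether extra pessary events came from the device or from the extra exam.

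**Working it through.** **Sample size for the illustration.** The documents give no figure for AEs, so I take the numbers per arm from the Sample Size Estimate. Its 138 reproduces with the unpooled formula for 50% versus 25%, two-sided 5% (sidedness is my assumption) and 80% power: n = (1.960 + 0.842)² × (0.25 + 0.1875) / 0.25² = 54.9, so 55 per arm; 55 / 0.80 = 68.75, so 69 per arm and 138 in total. I use 55 completers per arm.

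**Assumptions (none is in the documents).** True harm is equal in the arms. b is the share of women with an AE that both arms would detect; s is the share with a silent lesion at week 2; h is the share of those lesions gone by week 4. The exam finds every lesion present. The endpoint is any AE per woman, which the plan does not define.

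**Formulas.**
- Pessary recorded rate: 1 − (1 − b)(1 − s)
- Impressa recorded rate: 1 − (1 − b)(1 − s(1 − h))
- Expected excess of pessary women: n(1 − b)sh

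**Central case, n = 55, b = 15%, h = 50%.** Rejection rates come from exact binomial enumeration at two-sided 0.05.

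| s | Pessary | Impressa | Excess women | Chi-square | Fisher |
|---|---|---|---|---|---|
| 2% | 16.7% | 15.9% | 0.47 | 5.2% | 2.7% |
| 5% | 19.3% | 17.1% | 1.17 | 6.1% | 3.3% |
| 10% | 23.5% | 19.3% | 2.34 | 8.5% | 5.2% |
| 15% | 27.8% | 21.4% | 3.51 | 12.1% | 8.2% |

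For example, at s = 10%: 55 × 0.85 × 0.10 × 0.5 = 2.34.

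**Sensitivity.**
- No healing and full attendance: excess 0, chi-square about 5.0% to 5.1%.
- A quarter healed, s = 5% to 15%: 0.58 to 1.75 women, chi-square 5.3% to 6.6%.
- All healed, b = 15%, s = 15%: 7.01 women, chi-square 37.7%.
- All healed, b = 5%, s = 15%: 19.25% versus 5%, 7.84 women, chi-square 65.7%, Fisher 52.8%.
- Half healed, s = 15%: chi-square 17.5% at b = 5% and 9.0% at b = 30%.
- Dropout: if the whole 20% left between weeks 2 and 4, at most 69 × 0.20 × s further women, which is 0.28 at s = 2% and 2.07 at s = 15%.

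**Two effects that a comparison on common sources does not remove** (b = 15%, s = 10%, h = 50%).
- Repeat reports. A pessary user told of a lesion at week 2 may tick it at week 4; the AE item as printed has no recall window. If a share r of healed lesions is repeated, the excess is r × 2.34: 0, 1.17 and 2.34 women at r = 0, 50% and 100%.
- Findings acted on. If a share a of the lesions that would have persisted resolves because it was acted on, the week-4 comparison moves towards the pessary by n(1 − b)s(1 − h)a. At a = 50% this is 55 × 0.85 × 0.10 × 0.5 × 0.5 = 1.17 women.
- Both together, a = 50% and r = 50%. Pessary lesions gone by week 4 are 5% + 2.5% = 7.5%; half repeated is 3.75%; with 2.5% still present, 6.25% count, against 5% for Impressa. The excess is 55 × 0.85 × 0.0125 = 0.58 women, while the all-source excess is 2.34. Both are positive although true harm is equal.

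**The case against.** The difference in exams is deliberate. The pessary exam is routine care, the Interventions section aims at typical use, and the Participant Cost section notes that Impressa is bought without a physician. AEs as they surface in each device's usual pathway are a legitimate quantity. Detection is otherwise shared, the outcome is secondary, and the plan already accepts that secondary comparisons may be underpowered. In the milder scenarios the error rate is close to nominal, and Fisher's test, which the plan allows, stays at or below 5.2% in the central case up to s = 10%. An Impressa user examined for another complaint can also have a silent lesion found, which narrows the gap.

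Most of this stands, and it keeps the point small. It does not remove it: a reason for unequal care does not make unequally ascertained counts comparable, and low power adds noise but does not cancel a shift in one direction.

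A reader might infer that the AE comparison is invalid, or that Impressa users go unexamined. The documents do not support that: all women are examined at week 4 and asked the same AE questions twice. A reader might also infer that the primary result is biased by this route. It is not: the PGI-I is a patient rating at week 4 and does not depend on exam findings.

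**Conclusion.** The point holds in a limited form. As written, the plan can raise the pessary AE rate through detection alone, but only through silent lesions that are gone by week 4 or that occur in women who leave before then. Under the central assumptions that means 0.5 to 3.5 extra pessary women among 55, with chi-square rejecting in 5% to 12% of trials (Fisher 3% to 8%). The size is zero if no lesion heals and all attend, and larger with a lower base rate or complete healing. The documents cannot say where in that span the trial lies. The 66% scenario shows how the result depends on assumptions and should not be read as a forecast.

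It would also be tempting to treat an all-source display and a common-source display as limits that must contain the true difference. The last calculation above shows that they need not. This is a cheap improvement to a secondary outcome, to be considered, with medium confidence.

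**What to change.** Keep visits and care unchanged.

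1. Have the week-2 questionnaire completed before any exam. For each AE record the visit and the route of first detection: self-report, symptom-prompted exam or routine exam, including exams at early refit visits.
2. Make the between-arm comparison on sources applied alike in both arms: questionnaire and call-in self-reports, and separately the week-4 exam findings.
3. List descriptively the pessary findings first seen at a routine exam before week 4 in symptom-free women. Flag any later self-report of the same finding as a repeat, so its influence on the self-report comparison can be seen.
4. Show all-source AE rates by arm and route alongside, and state the unequal week-2 exam as a limitation. Do not present the two displays as a range that must hold the true difference.

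The cost is a paragraph in the plan, a form field and a fixed order of questionnaire and exam; no exams are added. The route field is best in place before data are collected, and the rule before AE data are analysed. The downside is that some clinician-confirmed pessary findings leave the formal comparison, for the device the investigators expect to do better. A week-2 finding that was acted on and resolved could also favour the pessary at week 4. Both displays must therefore be shown.
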